### **Supportive analyses**

The primary analysis will be repeated for Day 15. The proportion of patients who died, developed respiratory failure, or received ICU care by Day 15 will be analyzed with the same logistic regression model as for the primary endpoint.

The primary analysis will be repeated for each and combinations of the three events in the composite endpoint: death, respiratory failure (requires mechanical ventilation), ICU care, respiratory failure (or death), and ICU care (or death). Separate logistic regression models will be fit to compare the odds between treatment groups for each of the endpoints. Missing data will be handled similarly as outlined for the primary analysis. The estimated odds ratios, p-values, and 95% CIs will be presented. The analyses will be performed for up to Day 15 and Day 29 respectively. The between group difference in these endpoints will also be assessed by risk difference using the marginal standardization method ([Ge et al 2011](#)).

The subgroup analyses (subgroups defined in [Section 2.2.1](#)) will be explored for the primary estimand and the same logistic regression model as described for the primary analysis with the additional term of subgroup factor (if not already included in the model) and the interaction term of subgroup and treatment. In case of analyses on subgroups with extremely imbalanced sample sizes, the subgroup levels can be combined, if appropriate, while fitting the analysis model, or Firth's penalized maximum likelihood estimation will be performed. The point estimate and 95% CI for odds ratio for each subgroup will be presented using forest plots.

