### 2.2.1 Subgroup of interest

Subgroup analyses are conducted to assess consistency of the treatment effect among the subgroups, without multiplicity adjustments. The following subgroups will be evaluated for the primary endpoint, i.e., defined as the proportion of patients who die, develop respiratory failure (require mechanical ventilation), or require ICU care by Day 29:

- Age category (< 18, 18 - < 65, ≥ 65 years)
- Gender (male, female)
- Race (White, Asian, Black, other)
- Ethnicity (Hispanic, non-Hispanic)
- Region (North America, East Europe, West Europe, and Latin America)
- Body mass index (BMI) ( $\leq 30.0 \text{ kg/m}^2$ ,  $> 30.0 \text{ kg/m}^2$ )
- Baseline steroid use (Yes, No)

- Baseline clinical status based on 9-point scale (3, 4, 5)
- Baseline hypertension (Yes, No)
- Baseline diabetes (Yes, No)
- [REDACTED]
- Time between onset of COVID-19 symptoms and randomization ( $\leq 10$ ,  $> 10$  days)

Baseline steroid use is defined as usage between onset of symptoms and randomization (inclusive). Baseline hypertension/diabetes is defined as “Yes” if patients have the comorbidity ongoing at randomization.

In addition to the primary endpoint, subgroups of patients with different baseline clinical status based on 9-point scale (3, 4, 5) will be evaluated for the following endpoints:

- Mortality by Day 29

• [REDACTED]

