## 2.5.3 Handling of missing values/censoring/discontinuations

If there is any missing data over 1-29 days, the patient will be considered as meeting the primary composite endpoint, unless they are in one of the scenarios below:

- There was no occurrence of death, respiratory failure (require mechanical ventilation), nor ICU care in all the available data and patients were discharged from the hospital.
- The last available observed data is from Day 15 or later, and there was no occurrence of death, respiratory failure (require mechanical ventilation), nor ICU care in all the available data.

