### **Inferential statistics for the clinical status**

The odds of observing a better category (lower number) of clinical status at Day 15 will be analyzed with a proportional odds model (POM). The odds ratio for treatment group (ruxolitinib + SoC therapy vs. placebo + SoC therapy) estimated from the POM can be interpreted as a summary of the odds ratios obtained from separate binary logistic regressions using all possible cutoff points of the ordinal outcome (e.g. the cutoff of level 5 ‘Non-invasive ventilation or high-flow oxygen’ will combine levels 0, 1, 2, 3, and 4 versus combined levels 5, 6, 7 and 8). The assumption of POM is that the effect of treatment is identical across all possible cutoff points of the ordinal outcome. The proportional odds assumption will be checked by a score test. The model will include treatment group, region, age, gender, and baseline clinical status ( $\leq 3$ ,  $\geq 4$ ) as covariates. The estimated odds ratios, p-values and 95% confidence intervals will be presented. The analysis will be repeated for the data at Day 29.

Missing data at Day 15/29 will not be imputed and thus will be excluded from the analysis.

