### **Time to improvement from baseline category**

Time to improvement from baseline category to one less severe category of the ordinal scale will be analyzed using a competing risk analysis framework where death will be treated as a competing risk. Specifically, a proportional hazards model for the subdistribution ([Fine and Gray 1999](#)) of time to improvement will be performed. Same covariates will be used as for the primary analysis. Patients who did not achieve improvement and did not die will be censored at their last clinical status assessment date. The estimated hazard ratios, p-values, and 95% CIs will be presented. The cumulative incidence functions of improvement and death over study days will be plotted by treatment.

In addition, the median time to improvement by treatment as well as the 95% CI will be estimated using the Kaplan-Meier approach, while dead patients will be censored at the maximum follow-up time in the study.

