#### **2.7.1.3 In-hospital outcomes**

Duration of hospitalization (time to hospital discharge) will be analyzed using a competing risk analysis framework (death will be treated as a competing risk). Specifically, a proportional hazards model for the subdistribution ([Fine and Gray 1999](#)) of time to hospital discharge will be performed. Same covariates will be used as for the primary analysis. Patients who were not discharged and did not die will be censored at their last assessment date. The estimated hazard ratios, p-values, and 95% CIs will be presented. The cumulative incidence functions of hospital discharge and death over study days will be plotted by treatment.

In addition, the median time to hospital discharge by treatment as well as the 95% CI will be estimated using the Kaplan-Meier approach, while dead patients will be censored at the maximum follow-up time in the study.

The analyses of mortality rates at Day 15 and at Day 29, and proportion of patients requiring mechanical ventilation by Day 29 are described in [Section 2.5.4](#).

The subgroups of patients with different baseline clinical status will be evaluated for mortality using a similar logistic regression model as described for the primary analysis, replacing the baseline clinical status ( $\leq 3, \geq 4$ ) by baseline clinical status as a categorical variable, and adding

the interaction term of baseline clinical status and treatment. The point estimate and 95% CI for odds ratio for each subgroup will be summarized.

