## **2.8.2 Deaths**

Fatal AEs will be summarized and listed as specified in [Section 2.8.1](#).

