## 4 Change to protocol specified analyses

The analysis of the primary endpoint is the same as in the protocol. However, the handling of missing data for the primary composite endpoint is worded differently from the protocol. As the protocol allows patients to be treated for 14 or 28 days some of the patients will not be treated for the entire study period of 29 days because they have recovered and/or been discharged or the investigator feels they would not benefit from further double-blind treatment. Such cases did not “discontinue from the double-blind treatment”, but they actually “completed the planned treatment”. The off-treatment measurements collected should be used in the analysis (which did not change from the protocol) wherever available, as the outcome is still valid as a result of the previous treatment. In addition, the off-treatment data collected for other patients will also be used, from an intention-to-treatment perspective. The rationale of the missing data handling is made clearer in the SAP.

In Section 12.3 of the protocol, it was mentioned that significant non-drug therapies will be summarized according to the ATC classification system. However in the SAP, we specify that surgical and medical procedures will be summarized by primary SOC and PT, as ATC classification is not available for non-drug therapies.

In Section 12.4.2 of the protocol, it was mentioned that baseline clinical status based on the 9-point scale ( $\leq 4$ ,  $\geq 5$ ) will be included as a covariate in the primary analysis model. In the SAP, we have changed the categorization of the score to be ( $\leq 3$ ,  $\geq 4$ ). This is because very limited patients were recruited with baseline clinical status of 5 and the potential issues it may cause in the modeling.

In Section 12.5.1 of the protocol, it was mentioned that country will be used as a covariate. However, we have modified in the SAP that region will be included instead. This will avoid potential modeling issues due to small sample size in some of the countries.

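### The composite's rule that missing data count as an event is carried into the death, ventilation and ICU models, so some patients lost early would be reported as deaths nobody observed

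*SAP*

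**What the plan says.** SAP 2.5.3 sets the default for the composite: "If there is any missing data over 1-29 days, the patient will be considered as meeting the primary composite endpoint". There are two exceptions. Both require that none of the three events appears in the available data. The patient must also have been discharged, or have been last observed on Day 15 or later.

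SAP 2.5.4 repeats the primary analysis for death, respiratory failure and ICU care separately, and for two combinations with death, at Day 15 and Day 29. For all of these: "Missing data will be handled similarly as outlined for the primary analysis".

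SAP 2.7.1.3 gives no separate method for "The analyses of mortality rates at Day 15 and at Day 29, and proportion of patients requiring mechanical ventilation by Day 29"; it refers back to 2.5.4. SAP 2.2.1 also lists "Mortality by Day 29" for subgroup analysis by baseline clinical status.

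Elsewhere deaths are not imputed. For the proportional odds model, in which score 8 is death: "Missing data at Day 15/29 will not be imputed and thus will be excluded from the analysis". The change-from-baseline ANCOVA does the same. Time to improvement is analysed in a model "where death will be treated as a competing risk", and patients who neither improved nor died are censored. SAP 2.8.2 summarises reported fatal adverse events.

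SAP Section 4 notes that "the handling of missing data for the primary composite endpoint is worded differently from the protocol". It does not mention the single components.

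**The concern.** For a three-part composite, counting an unresolved inpatient as a failure is a recognisable conservative convention. For death alone, it records a fact that nobody observed. The same patient also becomes a ventilation event in one model and an ICU event in another.

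At stake is the plan's only mortality-specific inference: the odds ratio, the risk difference and the subgroup analysis by baseline status. Its death count could disagree with those in the ordinal-scale analyses, the competing-risk models and the safety summaries. SAP 2.5.4 does not ask for the number of imputed deaths by arm. The tipping-point and multiple-imputation analyses cover only the composite, so neither would show the effect on mortality.

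**Working it through.** **Applying the rule.** Take a patient in hospital, with no event recorded, who withdraws consent on Day 8. Protocol 9.1.3 treats later data as missing. The patient was not discharged and was last seen before Day 15, so neither exception applies and the default is an event. In the death-only model that event is death, at both Day 15 and Day 29.

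Two readings of the word *similarly* are possible:

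- *Component substituted* (the exceptions reworded to no death observed). This patient is still coded dead.
- *Literal.* Both exceptions require none of the three events. A patient with earlier ICU care or ventilation and any later missing data is then also coded dead, even if last seen alive after Day 15.

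SAP 2.5.3 is written for Days 1-29 and has no Day 15 version.

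**Inputs.** Arm sizes are 134 placebo and 268 ruxolitinib (SAP 1.1). The plan's power table concerns only the composite. It reproduces with these arm sizes and an unpooled two-proportion z-test: 91.3, 85.2, 82.1, 82.1, 85.2 and 91.3%, against the stated 91, 85, 82, 82, 85 and 91%. There is no stated mortality or dropout figure to reproduce, so the rates below are assumptions. Let m be true mortality and d the share of an arm that is event-free, in hospital and lost before Day 15.

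Reported rate r = m + (1 - m)d; imputed deaths = n(1 - m)d.

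**Equal loss, m = 5% placebo and 2.5% ruxolitinib.** True OR = (0.025/0.975)/(0.05/0.95) = 0.49. True risk difference is -2.50 points. True deaths = 134 × 0.05 + 268 × 0.025 = 13.4.

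| d (patients of 402) | Reported rates, placebo / ruxolitinib | OR | Risk difference (points) | Imputed deaths | Share of reported deaths |
|---|---|---|---|---|---|
| 0.5% (2) | 5.47% / 2.99% | 0.53 | -2.49 | 1.9 | 13% |
| 1% (4) | 5.95% / 3.48% | 0.57 | -2.48 | 3.9 | 22% |
| 2% (8) | 6.90% / 4.45% | 0.63 | -2.45 | 7.8 | 37% |

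For d = 1%: placebo 0.05 + 0.95 × 0.01 = 5.95%; ruxolitinib 0.025 + 0.975 × 0.01 = 3.475%; imputed deaths 134 × 0.95 × 0.01 + 268 × 0.975 × 0.01 = 3.9; 3.9/(13.4 + 3.9) = 22%.

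**Unequal loss, no true effect, m = 3% in both arms.** Reported rates are 3.49% (d = 0.5%), 3.97% (1%) and 4.94% (2%). The chance of p < 0.05 (two-sided) comes from exact enumeration of both binomials, using the unadjusted log-OR Wald test (a zero cell counts as no rejection) and the pooled Pearson test.

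| Loss, placebo vs ruxolitinib | OR | Wald | Pearson |
|---|---|---|---|
| none | 1.00 | 2.6% | 4.7% |
| 0.5% vs 1% | 1.14 | 2.3% | 4.8% |
| 1% vs 0.5% | 0.87 | 4.6% | 6.1% |
| 1% vs 2% | 1.26 | 3.5% | 5.9% |
| 2% vs 1% | 0.80 | 7.0% | 8.3% |

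**Leaving unknown status out instead.** In the 2% vs 1% case about 131 and 265 patients remain, the OR is 1.00 and Wald rejection is about 2.5%. If lost patients die at k times the average rate and overall mortality stays at m, mortality among the rest is s = (m - d·k·m)/(1 - d). Missing = dead then reports d + (1 - d)s.

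For k = 5: s = (0.03 - 0.02 × 0.15)/0.98 = 2.76% on placebo and (0.03 - 0.01 × 0.15)/0.99 = 2.88% on ruxolitinib, giving OR 1.05. Missing = dead gives 4.70% and 3.85%, OR 0.81. For k = 3 the two ORs are 1.02 and 0.80. With true mortality 5% and 2.5%, d = 1% and k = 5, exclusion gives OR 0.49 and missing = dead gives 0.57.

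The planned covariate-adjusted model was not simulated.

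**The case against.** **The wording is loose and the group is tiny.** *Similarly* is not *identically*. Inpatients are assessed daily, event-free discharged patients are exempt, and stopping treatment is not withdrawal (Protocol 9.1.1). The 2% vs 1% case rests on about 2.6 imputed deaths per arm. Nothing in a double-blind trial with matching placebo suggests that in-hospital withdrawal should differ by arm. All of this is fair and limits the size. It does not remove the problem: either reading of *similarly* codes this patient as dead, and neither document offers another rule.

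**Other outputs would show a discrepancy.** Cumulative incidence of death, daily status distributions and fatal adverse events are all planned from observed data. They would reveal a mismatch but not explain it, and the inferential mortality result would still be the one with imputed deaths.

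**Exclusion has weaknesses too.** It departs from analysing the whole randomized set. It also keeps an asymmetry: an inpatient last seen on Day 15 counts as alive at Day 29, while one last seen on Day 14 is left out. And it can be the worse rule. In the 2% vs 1% case, if 40% of lost patients die, the two rules err about equally (OR 1.17 for exclusion, 0.85 for missing = dead); at 50% exclusion is worse (1.24 against 0.87). These points stand as limits. The Day 15 allowance is already in the plan, such mortality is far above the assumed 3% average, and missing = dead should be kept as a sensitivity analysis for that possibility.

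**Conclusion.** The concern holds. As written, the plan codes an event-free inpatient last observed before Day 15 as dead in the mortality models, and as a ventilation and ICU event in the others. With equal loss the mortality odds ratio is pulled toward 1 while the risk difference hardly moves; with unequal loss a spurious difference can appear in either direction. Of the four unequal-loss cases, only 2% vs 1% takes the Wald rejection rate above 5%.

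All sizes rest on assumed mortality and loss rates and on unadjusted tests. Below about 0.5% loss the effect is small. The primary test is not affected. There is no key secondary objective and no multiplicity control, so this is a bias in named secondary endpoints. It should be fixed before unblinding but does not threaten the trial's main conclusion.

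**What to change.** Replace the missing-data sentence in SAP 2.5.4 with a component-specific rule:

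1. **Death by Day 15 / Day 29.** Event: documented death by that day. Non-event: known alive on or after that day; or no death in the available data and either discharged or, for Day 29 only, last observed on Day 15 or later. The remaining patients are not set to dead. Leave them out of the main mortality model, state the assumption (given the covariates, their death risk is like that of patients with known status), and report their number by arm.
2. **Ventilation and ICU care.** Same structure with the component substituted. A documented event counts whatever is missing later. A patient who died without the component is a non-event in the single-component model and an event in the already planned version combined with death, shown alongside. Unknowns are neither events nor silent non-events and are reported by arm.
3. **Sensitivity.** Keep missing = event for each component as a labelled worst-case analysis.
4. **Subgroups.** Use the same mortality variable in the baseline-status analysis (SAP 2.2.1 and 2.7.1.3).
5. **Record.** Add an entry to SAP Section 4, because Protocol 12.4.7 describes the component analyses as repeats of the primary analysis.

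The cost is SAP wording, a small programming change and that one entry. The logistic model and risk difference stay, and Protocol 12.4.4 already leaves other missing-data rules to the SAP. The downside is that a few patients leave the main component models; the worst-case analysis keeps them.

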## 2.6 Analysis of the key secondary objective

There is no key secondary objective defined in the protocol.

## 2.7 Analysis of secondary efficacy objectives

### 2.7.1 Secondary endpoints

No multiplicity adjustment will be carried out for secondary analyses described below.

All analysis of secondary endpoints will be performed on the RAS.

#### 2.7.1.1 9-category ordinal scale

The clinical status of the patient is assessed using a 9-category ordinal scale ([WHO 18-Feb-2020](#)). The scale is as follows:

Patient State	Descriptor	Score
Uninfected	No clinical or virological evidence of infection	0
Ambulatory (defined as not in hospital or in hospital and ready for discharge)	No limitation of activities	1
	Limitation of activities	2
Hospitalized Mild Disease	Hospitalized, no oxygen therapy (defined as SpO 2 ≥ 94% on room air)	3
	Oxygen by mask or nasal prongs	4
Hospitalized Severe Disease	Non-invasive ventilation or high-flow oxygen	5
	Intubation and mechanical ventilation	6
	Ventilation + additional organ support – pressors, RRT (renal replacement therapy), ECMO (extracorporeal membrane oxygenation)	7

Dead	Death	8
-------------	-------	---

The baseline value is defined as the last assessment of clinical status prior to first dose of double-blind treatment. If missing, the baseline value will be assumed to be missing at random as assessments are performed prior to any knowledge of treatment allocation and will be imputed using the median value of all patients with non-missing baseline values in the RAS.

### **Descriptive statistics**

Summary statistics (mean, median, standard deviation, q1, q3, min, max, frequencies and percentages in each category) of clinical status at baseline, Day 15, and Day 29 as well as change from baseline at Day 15 and Day 29 will be summarized by treatment arm.

The mean clinical status on a daily basis over 29 days will be plotted by treatment arm with the 95% confidence interval. A stacked bar chart will also be plotted to display the distribution of clinical status on a daily basis over 29 days.

No imputation will be done for missing data.

### **Inferential statistics for the clinical status**

The odds of observing a better category (lower number) of clinical status at Day 15 will be analyzed with a proportional odds model (POM). The odds ratio for treatment group (ruxolitinib + SoC therapy vs. placebo + SoC therapy) estimated from the POM can be interpreted as a summary of the odds ratios obtained from separate binary logistic regressions using all possible cutoff points of the ordinal outcome (e.g. the cutoff of level 5 ‘Non-invasive ventilation or high-flow oxygen’ will combine levels 0, 1, 2, 3, and 4 versus combined levels 5, 6, 7 and 8). The assumption of POM is that the effect of treatment is identical across all possible cutoff points of the ordinal outcome. The proportional odds assumption will be checked by a score test. The model will include treatment group, region, age, gender, and baseline clinical status ( $\leq 3$ ,  $\geq 4$ ) as covariates. The estimated odds ratios, p-values and 95% confidence intervals will be presented. The analysis will be repeated for the data at Day 29.

Missing data at Day 15/29 will not be imputed and thus will be excluded from the analysis.

### **Change from baseline in clinical status**

#### Responder analysis

The treatment groups will also be compared in terms of at least a one-point improvement, at least a two-point improvement, and at least a one-point deterioration in clinical status at Days 15 and 29 using respective logistic regression models with the same covariates as for the POM. The estimated odds ratios, p-values, and 95% CIs will be presented.

If a patient has missing data at Day 15/29, the patient will be treated as a non-responder in the respective analysis.

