4.3 Rationale for dose/regimen and duration of treatment

The ruxolitinib dose regimen chosen in this study is the lowest efficacious dose based on pharmacokinetic data. Ruxolitinib 5 mg twice daily is the approved starting dose for treatment of steroid-refractory acute graft versus host disease in the US with demonstrated anti-inflammatory effect ([Jagasia et al 2020](#)). Ruxolitinib 5 mg twice daily is also the starting dose recommended for patients with myelofibrosis when platelets are $50 \times 10^9/L - <100 \times 10^9/L$.

[Cao et al \(2020\)](#) reported the median hospital stay for COVID-19 was 12 days with an interquartile range of 1 to 14 days. Therefore, a duration of treatment for 14 days seems reasonable and has been selected for this study. An additional 14 days of study drug may be given, if in the opinion of the investigator, the patient's clinical signs and symptoms are not improved or worsen and the potential benefit outweighs the potential risk.

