When possible, the sequence of assessments at each visit should be as follows (at visits required in the schedule of assessments).

- Efficacy assessments: clinical status, clinical signs and symptoms, oxygen saturation, consciousness, ventilatory status;
- Safety assessments: vital signs, review of adverse events, concomitant medications;

Laboratory samples: on days indicated in schedule of assessments.

Results from tests or examinations done as part of routine care prior to the screening visit may be used for the study as indicated in [Table 8-1](#) (Assessment Schedule). **However, the above-mentioned efficacy assessments (clinical status, clinical signs and symptoms, oxygen saturation, consciousness, ventilatory status) must be done in the morning of randomization between 7 AM and 12 PM, prior to administering study drug.**

If a patient is discharged from the hospital during the study period, the Clinical Status Evaluation with 9-point ordinal scale will be performed via telephone call (between 7 AM and 12 PM local time) daily except for Day 15 and Day 29 when it will be performed in clinic. For Day 15 and Day 29, if an in-clinic visit is not possible, the visit may be performed in an appropriate setting, including at home, with appropriate study personnel.

Table 8-1 Assessment Schedule

All assessments will be obtained while patient is in hospital. Once patient is discharged, assessments will be done via the telephone as indicated in the table below with the exception of Day 15 and Day 29 which require in-clinic assessments. For Day 15 and Day 29, if an in-clinic visit is not possible, the visit may be performed in an appropriate setting, including at home, with appropriate study personnel.

Study Day	Screening	Study Period				
	Screening	Day 1 (Randomization)	Day 2-14 (every day unless otherwise specified below)	Day 15	Day 16-28 (every day unless otherwise specified below)	Day 29 (End of study)
Informed consent (and assent if applicable) ¹	x					
Inclusion / Exclusion criteria	x	x				
Demographics / medical history (including co-morbidities checklist)	x					
SARS-CoV-2 virus confirmation ²	s					
Vital signs ³ (between 7 AM and 12 PM local time)	x ⁴	x	x (while in hospital)	x	x (while in hospital)	x
SpO ₂ assessment (between 7 AM and 12 PM local time – done at same time as vital signs)	x ⁴	x	x (while in hospital)	x	x (while in hospital)	x

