SpO ₂ assessment on room air (for patients on oxygen by nasal cannula (≤ 2L/min) (based on investigator medical judgement) (between 7 AM and 12 PM local time – done at same time as vital signs)			(only on day of discharge)	x	(only on day of discharge)	x
FiO ₂ assessment (between 7 AM and 12 PM local time – done at same time as vital signs)	x ⁴	x	x (while in hospital)	x	x (while in hospital)	x

Study Day	Screening	Study Period				
	Screening	Day 1 (Randomization)	Day 2-14 (every day unless otherwise specified below)	Day 15	Day 16-28 (every day unless otherwise specified below)	Day 29 (End of study)
Consciousness assessment (between 7 AM and 12 PM local time – done at same time as vital signs)		x	x (while in hospital)	x	x (while in hospital)	x
Clinical Status Evaluation with 9-point ordinal scale (if patient is discharged to home, telephone call daily except for Day 15 and Day 29 when in clinic) (between 7 AM and 12 PM local time)		x	x (via telephone if not in hospital)	x	x (via telephone if not in hospital)	x
Height (measured or patient or guardian/health proxy reported), weight, BMI	x ⁴					x
Physical exam	s ⁴					
Ventilatory status (e.g. mechanical ventilation, supplemental oxygen, intubation and non-invasive ventilation [e.g. CPAP, BIPAP, etc.]	x ⁴	x	x (via telephone if not in hospital)	x	x (via telephone if not in hospital)	x
Drug dispensation and administration		x	Days 2-14	x (if applicable)	Days 16-28 (if applicable)	x (if applicable)
Assessment of re-treatment (if second course of 14 day treatment is needed)				s		
Reconcile study medication				s		s
Collect unused study medication				s		s
Hematology ⁵ (local labs)	x ⁶	x ⁷	Days 3, 5, 7, 9, 11, 13 (while in hospital)	x	Days 17, 19, 21, 23, 25, 27 (while in hospital)	x
Clinical chemistry, [REDACTED] [REDACTED] ⁵	x ⁶	x ⁷	Days 3, 5, 7, 9, 11, 13 (while in hospital)	x	Days 17, 19, 21, 23, 25, 27 (while in hospital)	x

Study Day	Screening	Study Period				
	Screening	Day 1 (Randomization)	Day 2-14 (every day unless otherwise specified below)	Day 15	Day 16-28 (every day unless otherwise specified below)	Day 29 (End of study)
Serum pregnancy test (local labs); results must be reviewed prior to randomization	x ⁸					x
Chest x-ray (CXR) or chest CT scan ⁹	x					
ECG (local) ⁴	s					
Adverse events	x	x	x (via telephone if not in hospital)	x	x (via telephone if not in hospital)	x

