#### **2.7.1.2 Oxygen saturation**

The proportion of patients with no oxygen therapy (defined as having a clinical status score of 0, 1, 2, or 3, or oxygen saturation  $\geq 94\%$  when measured on room air) at Days 15 and 29 will be analyzed using logistic regression models with the same covariates as for the primary analyses, with baseline SpO2/FiO2 added. The estimated odds ratios, p-values, and 95% CIs will be presented.

Missing data at Day 15/29 will not be imputed and thus will be excluded from the analysis.

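### A discharged patient with no in-person score on Day 15 or Day 29 is counted as not improved, although being at home is itself an improvement on the scale

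*SAP*

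**What the plan says.** **Collection.** Protocol Section 8 has the clinical status of discharged patients taken by telephone "daily except for Day 15 and Day 29 when it will be performed in clinic". The clinical status row of Table 8-1 repeats this: "if patient is discharged to home, telephone call daily except for Day 15 and Day 29 when in clinic". The fallback is another in-person contact: "if an in-clinic visit is not possible, the visit may be performed in an appropriate setting, including at home, with appropriate study personnel". The study design text in Section 3 says the same. None of these places offers a telephone score on the two days.

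**A conflicting section.** Protocol 8.3.1 has discharged patients assessed by telephone with no exception for Days 15 and 29. It also obtains each day's score on the following day, so that the Day 2 score is obtained on Day 3.

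**Analysis.** The responder analyses in SAP 2.7.1.1 cover two improvement endpoints (at least 1 point, at least 2 points) and "at least a one-point deterioration in clinical status at Days 15 and 29 using respective logistic regression models". The missing-data rule for all three is: "If a patient has missing data at Day 15/29, the patient will be treated as a non-responder in the respective analysis". It has no exception for discharge, no visit window and no use of adjacent days.

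**Other analyses.** For the proportional odds model, the ANCOVA and the no-oxygen endpoint the SAP says: "Missing data at Day 15/29 will not be imputed and thus will be excluded from the analysis". For the primary endpoint, SAP 2.5.3 does not count a patient with missing data as a failure if the patient was discharged and had no component event in the available data.

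**The concern.** A discharged patient who makes neither the clinic visit nor an alternative visit can have telephone scores on neighbouring days and none on the analysis day. The responder rule then assigns an outcome that the scale rules out for a patient who is still at home. The same patient is dropped from the proportional odds and ANCOVA analyses, is treated favourably by the primary-endpoint rule, and counts as improved in the time-to-improvement analysis, which can use a score from any day.

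Two things are at stake. The estimated effect on the improvement endpoints would depend partly on attendance after discharge. The responder and ordinal analyses could also disagree for reasons unrelated to the drug.

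**Working it through.** **Step 1: what the scale implies.** Patients out of hospital fall in the ambulatory scores 1 or 2, or 0 if uninfected. The baseline scores that the SAP lists for subgroups are 3, 4 and 5.

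| Baseline | Smallest improvement if at home (score 2) | At least 1 point | At least 2 points |
|---|---|---|---|
| 3 | 3 − 2 = 1 | always met | depends on the score |
| 4 | 4 − 2 = 2 | always met | always met |
| 5 | 5 − 2 = 3 | always met | always met |

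For a patient still at home, non-response is wrong in every case for the 1-point endpoint. For the 2-point endpoint it is wrong from baseline 4 or 5. For deterioration, a non-responder read literally is someone who did not deteriorate, which is probably right after discharge.

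**Step 2: which day's score is lost if the visit is missed.**

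| Reading | Day 15 visit missed | Day 29 visit missed |
|---|---|---|
| Section 8 and Table 8-1, same-day score | Day 15 score lost; Day 14 and 16 calls exist | Day 29 score lost; Day 28 call exists |
| 8.3.1, next-day rule | Day 14 score lost; Day 15 score comes from the Day 16 call | Day 28 score lost; Day 29 score needs a Day 30 contact, which is not scheduled |

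Day 15 therefore depends on which section governs. Day 29 is exposed on either reading.

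**Step 3: reproduce the plan's power table.** SAP Table 3-1 concerns the primary endpoint; no power is stated for the responder endpoints. Inputs: 134 placebo and 268 ruxolitinib (SAP 1.1), two-sided 5%, a 15-point difference (SAP 3).

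Power = Φ(|p1 − p0| / SE − 1.96), with SE = √[p0(1 − p0)/134 + p1(1 − p1)/268].

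The six rows give 91.3, 85.2, 82.1, 82.1, 85.2 and 91.3%, against 91, 85, 82, 82, 85 and 91% stated. The formula reproduces the table.

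**Step 4: illustration with equal missed-visit rates.** Assumed, not in the documents: true improvement 60% placebo and 75% ruxolitinib; every improved patient discharged; a share m of them without a score in both arms. Observed rates are p0(1 − m) and p1(1 − m). The number miscoded is m × (134 × 0.60 + 268 × 0.75) = m × 281.4.

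| m | Observed rates | Odds ratio | Power | Miscoded of 402 |
|---|---|---|---|---|
| 0 | 60.0% vs 75.0% | 2.00 | 85.2% | 0 |
| 5% | 57.0% vs 71.25% | 1.87 | 79.9% | 14 |
| 10% | 54.0% vs 67.5% | 1.77 | 74.3% | 28 |
| 20% | 48.0% vs 60.0% | 1.63 | 62.7% | 56 |

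Worked row, m = 10%: SE = √(0.54 × 0.46/134 + 0.675 × 0.325/268) = 0.0517; 0.135/0.0517 − 1.96 = 0.65; Φ(0.65) = 0.74. Odds ratio = (0.675/0.325)/(0.54/0.46) = 1.77.

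Improvement from 5 to 4 or from 4 to 3 happens in hospital, so fewer responders than this are exposed. For a given m the table is an upper bound on the attenuation, provided the discharged share of improved patients is similar in the two arms.

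**Step 5: unequal rates.** Same true rates:
- 5% missing on placebo and 10% on ruxolitinib: 57.0% vs 67.5%, odds ratio 1.57.
- 10% on placebo and 5% on ruxolitinib: 54.0% vs 71.25%, odds ratio 2.11, above the true 2.00.
- No true effect, 80% in both arms, 10% missing in one arm only: (0.72/0.28)/(0.80/0.20) = 0.64 for that arm.

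**The case against.** The best defence is that few patients should be affected. The call is replaced by a visit that may take place at home, and Section 8 asks for visits as close to the planned day as possible. The in-person requirement has a purpose, since vital signs, oxygen saturation and laboratory samples are due on those days. Under 8.3.1 a missed Day 15 visit need not lose the Day 15 score at all. Counting missing as non-response is a common conservative choice. The endpoints are secondary, the primary endpoint already protects event-free discharged patients, and time to improvement and time to discharge still capture their recovery.

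Much of this stands. It limits the point to patients with no in-person contact and to two secondary endpoints, and it makes the Day 15 part conditional. It does not remove the point:
- The SAP gives no window that would let a rescheduled visit count.
- The telephone contact that Protocol 9.1.1 keeps up after treatment discontinuation does not list the ordinal score among its minimum data.
- Day 29 has no telephone route on either reading.
- A conservative rule is hard to defend where the scale already fixes the answer, and with unequal attendance it is not reliably conservative.

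Stronger readings are tempting and are not supported:
- A reader might infer that the score is simply switched off on the two days. It is moved to an in-person visit.
- A reader might take "the median hospital stay for COVID-19 was 12 days" (Protocol 4.3) to mean that over half of patients are affected by Day 15. At most that figure describes patients due a visit, not those who miss it. It comes from a cited study and does not say that stays ended in discharge alive.
- A reader might infer that only patients who did well miss these visits, so the bias always runs against the drug. A discharged patient may be readmitted, worsen or die, and step 5 shows bias in either direction.

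**Conclusion.** The point holds in a limited form. For a discharged patient still at home with no Day 15 or Day 29 score, the responder rule contradicts the scale for 1-point improvement and, from baseline 4 or 5, for 2-point improvement. It also runs opposite to the SAP's own rule for the primary endpoint. In the proportional odds and ANCOVA analyses the problem is selective exclusion, not miscoding.

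The primary endpoint, the sample size and the deterioration endpoint are not touched, and the improvement endpoints are secondary without multiplicity adjustment. The size cannot be derived from the documents. The odds ratios of 1.87 to 1.63 and power of 80% to 63% rest wholly on the assumed 60% versus 75%, equal missing shares of 5% to 20%, and every improved patient being discharged. They show how sensitive the result is and do not predict this trial's result. The Day 15 part depends on how 8.3.1 is reconciled; the Day 29 part does not. It should be corrected because the repair is specific and cheap.

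**What to change.** 1. **Reconcile Protocol 8.3.1 with Section 8 and Table 8-1** on the mode of assessment after discharge and on which day's score each contact records.
2. **Allow a telephone score.** Let the Day 15 and Day 29 clinical status be taken by telephone when no in-person visit occurs. If the next-day rule is kept, add a final contact for the Day 29 score.
3. **Amend SAP 2.7.1.1.** For a patient who is discharged, not known to be readmitted or dead, and without a Day 15 or Day 29 score, use the nearest available post-discharge telephone score within a stated window before applying the non-responder or exclusion rule. A window is safer than naming Day 14 or Day 28, because under the next-day rule those are the scores lost with the visit. Apply the same score in the responder, proportional odds and ANCOVA analyses, and keep the current rule as a sensitivity analysis. State what non-responder means for the deterioration endpoint.

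**Cost.** Items 1 and 2 need a protocol amendment with the approvals in Protocol 14.1. SAP Section 4 refers to patients already recruited, so they may come late. Item 3 is a short SAP text change, needs no new data and works alone if data collection is over. The downside is that a telephone or adjacent-day score replaces an in-person one for a few patients.
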